6.11.8.2.3. Analyses of Treatment-Emergent ADA on Specific Adverse Events

The analyses of TE-ADA effects on safety will be conducted on all evaluable patients within the defined Safety Population for Blinded Treatment Dosing Period (Period 2) and Combined Blinded Treatment Dosing and Extended Treatment Periods (Combined Periods 2 and 3).

Baseline definition for immunogenicity analyses for the Combined Treatment Period is the same as [Table RHCH.6.9](#).

AESIs of allergic reaction/hypersensitivity (anaphylaxis and non-anaphylaxis) and of injection-site reactions will be included in an assessment of AE to TE-ADA over time. Timing of an AE will be taken to be the reported AE start date.

For each TE-ADA status dichotomous variable (as defined in [Table RHCH.6.10](#)), patients will be categorized according to whether they were (i) always in lesser-TE-ADA status postbaseline or (ii) at some point postbaseline, were in greater-TE-ADA status. For each AESI, within the time-varying TE-ADA status groups, a summary will be provided of the number of patients who

had no event, events only while in lesser-TE-ADA status for group (i), or – for group (ii) – at least one event while in greater-TE-ADA status.

Additionally, summaries will be provided of the total number of AESI events (with unique start dates) by time-varying TE-ADA status groups at the event date. The summaries will aggregate time respectively in greater-TE-ADA status and in lesser-TE-ADA status, along with the event rates (rates per 100 patient-years) relative to those aggregate times.

By-patient listings will be provided of patients with TE-ADA who experience a treatment-emergent allergic reaction/hypersensitivity reaction or an injection site reaction.

6.12. Subgroup Analyses

6.12.1. Efficacy Subgroup Analyses

Subgroup analysis will be conducted for the primary endpoint of proportion of patients achieving an ASAS40 response at Week 16 (NRI) using the ITT Population for the Period 2. The major secondary efficacy endpoint, the proportion of patients achieving ASAS20 (NRI) at Week 16, will also be conducted. Subgroup analysis using the ITT Population in bDMARD-naïve patients may be explored.

For categorical response variables (ASAS20, ASAS40), a logistic regression analysis with treatment, subgroup, and treatment-by-subgroup interaction as factors will be used. The treatment-by-subgroup interaction will be tested at the 10% significance level. Treatment group differences will be evaluated within each subgroup using the Fisher's exact test, regardless of whether the interaction is statistically significant. If any group within the subgroup (for example, yes, no) is <10% of the total population, only descriptive statistics will be provided for that subgroup (that is, no inferential testing).

Forest plots may be created to illustrate the treatment differences with 95% CIs between each of the ixekizumab treatment groups and placebo group, by each subgroup category.

Please see [Table RHCH. 6.1.](#) for subgroups of baseline characteristics that will be analyzed.

Additional subgroup analyses on efficacy may be performed as deemed appropriate and necessary.

6.13. Protocol Deviations

Protocol deviations will be identified throughout the study. Important protocol deviations are defined as those violations from the protocol likely to have a significant impact on the completeness, accuracy, and/or reliability of the study data or that may significantly affect a subject's rights, safety, or well-being.

A separate document (known as the trial issue management plan) will be used to define the categories and subcategories of important protocol deviations, whether or not these deviations will result in the exclusion of patients from PPS, and the source of identification for the deviations.

The number and percentage of patients having important protocol deviations (s) will be summarized within category and subcategory of deviations by treatment group for:

- Period 2 (ITT Population);
- Period 3 (Extended Treatment Period Population).

A by-patient listing of important protocol deviations will be provided. A listing of protocol deviation due to COVID-19 will also be provided.

6.14. Interim Analyses

An interim database lock and unblinding will occur, and interim analyses will be performed at the time (that is, a cutoff date) the last patient completes Visit 8 (Blinded Dosing Treatment Period [Period 2], Week 16) or ETV. This interim database lock will include all data collected by the cutoff date including the data from the Extended Treatment Period (Period 3) and follow-up data from patients that have begun the Post-Treatment Follow-Up Period (Period 4). The analyses from the Week 16 lock will be treated as a primary analysis because all primary and major secondary study objectives will be assessed at this time.

Additional analyses and snapshots of study data may be performed during the Period 3 or after completion of Period 4 to fulfill the need for regulatory interactions or publication purposes.

Please see a separate blinding and unblinding plan document for the details.

6.15. Clinical Trial Registry Analyses

Additional analyses will be performed for the purpose of fulfilling the Clinical Trial Registry (CTR) requirements.

Analyses provided for the CTR requirements include summary of AEs, provided as a dataset which will be converted to an XML file. Both Serious Adverse Events and 'Other' Adverse Events are summarized: by treatment group, by MedDRA preferred term.

- An AE is considered 'Serious' whether or not it is a TEAE.
- An AE is considered in the 'Other' category if it is both a TEAE and is not serious. For each Serious AE and 'Other' AE, for each term and treatment group, the following are provided:
 - the number of participants at risk of an event
 - the number of participants who experienced each event term
 - the number of events experienced.
- Consistent with www.ClinicalTrials.gov requirements, 'Other' AEs that occur in fewer than 5% of patients/subjects in every treatment group may not be included if a 5% threshold is chosen (5% is the minimum threshold).
- AE reporting is consistent with other document disclosures such as the CSR.

7. Unblinding Plan

Refer to a separate blinding and unblinding plan.

8. References

- [ASAS] Assessment of Spondyloarthritis International Society. ASAS-Health Index users manual. Available at http://www.asas-group.org/clinical-instruments/asas_health_index/asas_hi_english_um.pdf. Accessed 25 March 2016.

Appendix 1. Algorithm for Determining ASAS Response

The following ASAS domains are used to determine ASAS40, ASAS20, ASAS partial remission, and ASAS5/6 (Sieper et al. 2009, ASAS Handbook), detailed definitions of ASAS40, ASAS20, ASAS partial remission, and ASAS5/6 are provided in [Table RHCH.6.3](#):

- Patient Global
- Spinal Pain
- Function
- Inflammation
- CRP and
- Spinal mobility (lateral spinal flexion).

The following variables will be derived for above domains as applicable:

Variables	Derivation / Comments	Imputation Approach with Missing Component
V1: Percent improvement from baseline	Calculated as: $100 \times \frac{\text{Percent improvement from baseline} = \text{Baseline score} - \text{Observed score}}{\text{Baseline score}}$ If a patient has experienced an improvement, this measure will be positive. If a patient has experienced a worsening in the condition, this measure will be negative.	Missing if baseline or observed value is missing
V2: Absolute improvement	Calculated as: Baseline score – Observed Score If a patient has experienced an improvement, this measure will be positive. If a patient has experienced a worsening in the condition, this measure will be negative.	Missing if baseline or observed value is missing
V3: Any worsening	Yes if V2 ‘absolute improvement’ is negative	Missing if V2 is missing
V4: Worsening of $\geq 20\%$ and ≥ 1 unit	Yes if $V1 \leq -20\%$ and $V2 \leq -1$	Missing if V1 or V2 is missing

Algorithm to calculate the *observed* ASAS40 response at a visit:

- **Step 1:** among the above 4 domains (patient global, spinal pain, function, and inflammation), if at least 3 of them are ≥ 40 on variable ‘percent improvement [V1]’ AND ≥ 2 on variable ‘absolute improvement [V2]’ AND variable ‘absolute improvement [V2]’ is ≥ 0 for the remaining domain, assign ASAS40 response as responder;
- **Step 2:** else, among the 4 domains, if any of them are ‘YES’ on variable ‘any worsening [V3]’, or at least 2 of them have nonmissing ‘percent improvement [V1]’ < 40 or nonmissing ‘absolute improvement [V2]’ < 2 , assign ASAS40 response as nonresponder;
- **Step 3:** For all other situations, assign ASAS40 response as missing.

Algorithm to calculate the *observed* ASAS20 response at a visit:

- **Step 1:** among the above 4 domains (patient global, spinal pain, function, and inflammation), if at least 3 of them are ≥ 20 on variable 'percent improvement [V1]' AND ≥ 1 on variable 'absolute improvement [V2]' AND variable 'Worsening of $\geq 20\%$ and ≥ 1 unit [V4]' is 'NO' for the remaining domain, assign ASAS20 response as responder;
- **Step 2:** else, among the 4 domains, if any of them are 'YES' on variable 'Worsening of $\geq 20\%$ and ≥ 1 unit [V4]', or at least 2 of them have nonmissing 'percent improvement [V1]' < 20 or nonmissing 'absolute improvement [V2]' < 1 , assign ASAS20 response as nonresponder;
- **Step 3:** For all other situations, assign ASAS20 response as missing.

Algorithm to calculate the *observed* ASAS partial remission response at a visit:

- **Step 1:** among the above 4 domains (patient global, spinal pain, function, and inflammation), if the value for all of them are not missing and ≤ 2 , then assign ASAS partial remission response as responder;
- **Step 2:** else, if at least one of the 4 domains have a value > 2 , assign ASAS partial remission response as nonresponder;
- **Step 3:** for all other situations, assign ASAS partial remission response as missing.

Algorithm to calculate the *observed* ASAS5/6 response at a visit:

- **Step 1:** among the 6 domains (Patient Global, Spinal Pain, Function, Inflammation, CRP, Spinal mobility), if at least 5 of them are ≥ 20 on variable 'percent improvement [V1]', then assign ASAS5/6 response as responder;
- **Step 2:** else, if any 2 or more domains have non-missing variable 'percent improvement [V1]' < 20 , then assign ASAS5/6 response as nonresponder;
- **Step 3:** for all other situations, assign ASAS5/6 response as missing.

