9.1.2.1.2. ASAS20

The ASAS20 is derived from patient-reported assessments. An ASAS20 response is defined as a $\geq 20\%$ improvement and an absolute improvement from baseline of ≥ 1 units (range 0 to 10) in ≥ 3 of 4 domains (Patient Global, Spinal Pain, Function, and Inflammation), and no worsening of $\geq 20\%$ and ≥ 1 unit (range 0 to 10) in the remaining domain.

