6.3.1. Nonresponder Imputation

Analysis of categorical efficacy and health outcome variables will be assessed using a NRI method. Patients will be considered nonresponders for the NRI analysis if they do not meet the clinical response criteria or have missing clinical response data at the primary analysis time point. All nonresponders at Week 16 (Visit 8), as well as all patients who discontinue study treatment at any time prior to Week 16 for any reason, will be defined as nonresponders for the NRI analysis at Week 16. Randomized patients without at least 1 postbaseline observation will also be defined as nonresponders for the NRI analysis.

The NRI may be applied at any time point specified for analysis.

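### SAP Appendix 1 has no rule for a domain score of 0 at baseline, so its ASAS20 algorithm cannot return responder for such a patient, even one who meets ASAS40

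*SAP*

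**What the plan says.** Protocol 9.1.2.1.2 and SAP Table RHCH.6.3 define ASAS20 as improvement of at least 20% and 1 unit in three of four domains (Patient Global, Spinal Pain, Function, Inflammation). The fourth domain blocks response only if it worsens by both 20% and at least one "unit (range 0 to 10) in the remaining domain". Table RHCH.6.3 sends the programmer to SAP Appendix 1 for the derivation.

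Appendix 1 uses these variables for each domain:

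- V1, percent improvement, has the baseline score as divisor. V2 is baseline minus observed. For both, the only missing rule is: "Missing if baseline or observed value is missing".
- V4 is YES when V1 is -20% or lower and V2 is -1 or lower. Its missing rule is: "Missing if V1 or V2 is missing".

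The ASAS20 steps are:

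- Step 1: three domains meet the thresholds and V4 "is 'NO' for the remaining domain, assign ASAS20 response as responder".
- Step 2: nonresponder if any V4 is YES, or if at least two domains have a nonmissing V1 below 20 or a nonmissing V2 below 1.
- Step 3: "For all other situations, assign ASAS20 response as missing".

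ASAS40 differs at Step 1. It asks only that V2 be at least 0 "for the remaining domain, assign ASAS40 response as responder".

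SAP 6.3.1 then applies to the result: "Patients will be considered nonresponders for the NRI analysis if they do not meet the clinical response criteria or have missing clinical response data".

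**The concern.** A domain that starts at 0 cannot improve, so it can only ever be the remaining domain. In ASAS20 that domain is judged by V4, V4 needs V1, and V1 has a zero divisor. A patient who satisfies the protocol definition can therefore fall through to Step 3 and be counted as a nonresponder. ASAS40, the stricter criterion, avoids the percentage for the remaining domain and classifies the same patient as a responder. A definition meant to be nested (ASAS40 within ASAS20) is then not nested in the derived data.

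ASAS20 at Week 16 in the overall population is Secondary 2 in the multiplicity-controlled family (SAP 6.4), so its derivation should match its definition in every case that the entry criteria allow.

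**Working it through.** The plan has no figure to reproduce here. The check follows Appendix 1 literally, with V1 taken as missing when the divisor is 0.

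**Can a zero baseline occur?** Protocol 6.1, criterion [3], requires BASDAI of at least 4 and back pain of at least 4 at screening and baseline. That in effect protects Spinal Pain. Patient Global and Function (BASFI) have no floor. Inflammation is the mean of BASDAI questions 5 and 6 and can also be 0: with questions 1 to 4 all at 5, BASDAI = (5+5+5+5+0)/5 = 4.0.

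**One patient.** Baseline: Patient Global 8, Spinal Pain 8, Inflammation 8, Function 0. Week 16: 3, 3, 3, 0.

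- First three domains: V1 = 100 × (8-3)/8 = 62.5% and V2 = 5. They pass the ASAS20 thresholds (20%, 1 unit) and the ASAS40 thresholds (40%, 2 units).
- Function: V1 = 100 × (0-0)/0 is undefined, V2 = 0, so V4 is missing.

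| Step | ASAS40 | ASAS20 |
|---|---|---|
| 1 | Function V2 = 0, which is at least 0: **responder** | Function V4 is missing, not NO: fails |
| 2 | not reached | no V4 is YES; only one domain (Function, V2 below 1) is below threshold and two are needed: fails |
| 3 | not reached | **missing** |
| After NRI | responder | **nonresponder** |

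Under the protocol definition this patient is an ASAS20 responder, because Function went from 0 to 0 and has not worsened.

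**A grid of patterns.** Function baseline was 0. The other three baselines were each 4, 6, 8 or 10, with observed scores 0 to 10. Observed Function was 0, 0.5, 1, 2, 5 or 10. This gives 4³ × 11³ × 6 = 511,104 patterns.

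- Appendix 1 as written: 0 patterns are ASAS20 responders. All 6,859 ASAS40 responders have ASAS20 missing. A further 86,891 ASAS40 nonresponders also have ASAS20 missing.
- Control with Function baseline 1 or 4: all 104,329 ASAS40 responders are ASAS20 responders. The zero divisor is therefore the cause.
- With V4 taken from V2 when baseline is 0: all 6,859 ASAS40 responders become ASAS20 responders, 24,391 other patterns become ASAS20-only responders, and none is missing.

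These counts test the logic. They say nothing about how often patients show such patterns.

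**Size.** At 70 per arm, one affected responder moves that arm's rate by 1/70 = 1.4 percentage points. The share of patients with a zero domain is not given. As an assumed range, 0% to 3% would be 0 to about 4 of 140 patients. If a share f of each arm is affected and response is independent of having a zero baseline (both assumptions), each rate is multiplied by (1-f), and so is the difference. With f = 3% and an illustrative 30-point difference, the loss is 0.03 × 30 = 0.9 points.

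**The case against.** The strongest reply is that the SAP nowhere says V1 is missing at a zero baseline. Its missing rule covers missing scores, and 0 is an observed score. For a domain that goes from 0 to 0, V2 = 0 already makes the V4 condition false whatever V1 is, and a sensible programmer would code NO. This stands in part: the failure comes from the zero divisor, which SAS (named in SAP 6.1) turns into a missing value, and not from an explicit instruction. But coding NO would depart from the written V4 rule. The SAP also shows elsewhere that it can address a zero baseline: in Table RHCH.6.3 the ASAS-NSAID50 derivation is limited to patients with a nonzero baseline score.

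The second reply is rarity, and it also stands. A Function score of 0 requires zero on every scored BASFI item. An Inflammation score of 0 requires questions 5 and 6 both at 0 while BASDAI still reaches 4. A patient is affected only if the other three domains respond as well.

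A reader might infer more than the documents support:

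- That the planned outputs would expose the inconsistency. The SAP plans separate ASAS20 and ASAS40 summaries, with no cross-tabulation of the two, so a slightly low ASAS20 rate would pass unnoticed.
- That the algorithm returns no result at all for these patients. Step 2 still returns nonresponder where that is right; only responder is out of reach.
- That Step 2 also needs repair. It does not: with a zero baseline, V2 is nonmissing and never above 0, so the domain already counts as not improved.
- That type I error is inflated. Baseline zeros precede treatment and can occur in either arm; under the assumptions above, the difference shrinks towards zero.

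**Conclusion.** The point holds as a gap in the ASAS20 derivation. For a patient whose Patient Global, Function or Inflammation score is 0 at baseline, Appendix 1 as written cannot return responder at any visit. If the other three domains qualify, the observed status is missing and becomes nonresponder under NRI, the primary method for this endpoint. In the categorical MMRM the status stays missing, and in the time-to-first-response analysis the patient never counts as an event.

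The effect is probably small: 1.4 points on one arm's rate per affected responder, with an unknown and likely low number of patients. The conclusion rests on V1 being treated as missing when its divisor is 0. The primary endpoint, ASAS40 in bDMARD-naïve patients, is not affected. The change is worth making because it removes a conflict with the protocol's own definition at almost no cost, and because the rule is better fixed before unblinding than chosen after.

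**What to change.** Add one rule to SAP Appendix 1 under V4: if the baseline domain score is 0, V4 is YES when V2 is -1 or lower, and NO otherwise. This treats any rise of at least 1 unit from 0 as meeting the 20% condition, which has no numerical value there. Leave Step 2 and the ASAS40 algorithm as they are.

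Add a programming check that every ASAS40 responder at a visit is also an ASAS20 responder at that visit.

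The cost is one sentence and one derivation line. No new data are needed, and no patient's ASAS40 status changes.

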9.1.2.6. Bath Ankylosing Spondylitis Metrology Index—Spinal Mobility

The BASMI is a combined index comprising the following 5 clinical measurements of spinal mobility in patients with r-axSpA (Jenkinson et al. 1994):

- Lateral spinal flexion
- Tragus-to-wall distance
- Lumbar flexion (modified Schrober)
- Maximal intermalleolar distance
- Cervical rotation.

The BASMI includes these 5 measurements that are each scaled to a score of 0 to 10 depending on the result of the assessment (BASMI linear function). The average score of the 5 assessments gives the BASMI linear result (van der Heijde et al. 2008; Sieper et al. 2009).

The BASMI must be assessed by a rheumatologist or health care provider who meets the qualifications for study assessment.

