When the MMRM is used, the model will include treatment, baseline CRP status, TNF inhibitors experience, baseline value, baseline value-by-visit, visit, and treatment-by-visit interaction as fixed factors (except for the analysis of CRP, see paragraph below). The covariance structure to model the within-patient errors will be unstructured. If the unstructured covariance matrix results in a lack of convergence, the heterogeneous Toeplitz covariance structure, followed by the heterogeneous autoregressive covariance structure, followed by the compound symmetry, will be used. This order is specified according to a decreasing number of covariance parameters in the structure. The Kenward-Roger method will be used to estimate the denominator degrees of freedom. The restricted maximum likelihood (REML) will be used. Type III tests for the least-squares (LS) means will be used for the statistical comparison; the 95% CI will also be reported. Treatment group comparison with placebo at Week 16 (Visit 8) and all other visits will be reported.

For the analysis of CRP, the MMRM model will include treatment, baseline CRP status, TNF inhibitors experience, visit, and treatment-by-visit interaction as fixed factors.

When the ANCOVA is used, the model will include treatment, baseline CRP status, TNF inhibitors experience, and baseline value. Type III sums of squares for the LS means will be used for the statistical comparison; the 95% CI will also be reported.

For variables that are not collected at each postbaseline visit, data may exist at visits where the variable was not scheduled to be collected, due to early discontinuation visits. In these situations, data from the early discontinuation visit that do not correspond to the planned collection schedule will be excluded from the MMRM analyses (Andersen and Millen 2013). However, the data will still be used in other analyses, including shift analyses, or modified baseline observation carried forward (mBOCF) endpoint analyses, and other categorical analyses.

For selective efficacy measures, percent improvement will be calculated as $100 \times (\text{baseline score} - \text{observed scores}) / \text{baseline score}$, unless specified otherwise. If a patient has experienced an improvement, this measure will be positive. If a patient has experienced a worsening, this measure will be negative.

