6.1.2. General Considerations for Analyses during the Extended Treatment Period (Period 3)

Unless otherwise specified, Period 3 starts at the first injection of study treatment at Week 16 (Visit 8) and ends on the date of Week 52 (Visit 17) or the ETV (between Weeks 16 and 52). For the efficacy and health outcome analyses, baseline is defined as the last available value before the first injection in Period 2 and, in most cases, this will be the value recorded at Week 0 (Visit 2).

Unless otherwise specified, for the safety analyses during Period 3, baseline is defined as the last available value before first injection of ixekizumab in Period 3. In most cases, this will be the measure recorded at Week 16 (Visit 8). For treatment-emergent adverse events (TEAEs), baseline is the events ongoing just prior to the first injection of the study drug injection at Week 16 (for placebo and ixekizumab patients).

The number and percentage of patients having categorical efficacy response (for example, ASAS40) will be summarized for all scheduled visits (Nonresponder Imputation, NRI), including Week 52 (Visit 17) during Period 3.

In addition, the number and percentage of patients achieving response on ASAS20 for those who did not achieve response at Week 16, and the number and percentage of patients maintaining response for those who achieved response at Week 16, will be summarized for all scheduled visits (NRI), including Week 52 (Visit 17) during Period 3. Similar summary will be provided for ASAS40.

Each continuous efficacy and health outcome score and change from baseline (or percent improvement) will be summarized at all scheduled visits, including Week 52 (Visit 17) using descriptive statistics (n, mean, SD, median, minimum and maximum). Missing data will be imputed using mBOCF method (Section 6.3.2).

The categorical safety measures will be summarized with incidence rates. The mean change of the continuous safety measures will be summarized at all scheduled visits.

6.1.3. General Considerations for Analyses during Combined Blinded Treatment Dosing Period and Extended Treatment Period (Combined Periods 2 and 3)

Selective efficacy and health outcome analyses will be performed for Combined Periods 2 and 3 for ITT Population who are randomized to ixekizumab at Week 0 (Visit 2). These analyses included the primary endpoint, all major secondary endpoints, as well as ASDAS<1.3, ASDAS clinically important improvement and major improvement, and MRI SIJ SPARCC score.

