SPARCC SIJ Structural Score (SSS)	SPARCC SIJ SSS score change from baseline for each of the 4 features: fat metaplasia, bone erosion, backfill and ankylosis.	ANCOVA with observed case analysis; ANCOVA with mBOCF	ITT Population	IXE80Q4W vs. placebo at Week 16	Other secondary efficacy analyses (Section 6.9.4).
		Descriptive statistics of change from baseline	Extended Treatment Period Population	No comparisons at Week 52	Other secondary efficacy analyses (Section 6.9.4).
ASAS	ASAS5/6 and ASAS partial remission	Logistic regression analysis with NRI; Fisher's exact test with NRI	ITT Population	IXE80Q4W vs. placebo at Week 16 and all other postbaseline visits in Period 2	Other secondary efficacy analyses (Section 6.9.4).
		Descriptive statistics of ASAS5/6 response rate and ASAS partial remission	Extended Treatment Period Population	No comparison during Period 3	Other secondary efficacy analyses (Section 6.9.4).
Patient Global	Patient Global change and % improvement from baseline	MMRM	ITT Population	IXE80Q4W vs. placebo at Week 16 and all other postbaseline visits in Period 2	Other secondary efficacy analyses (Section 6.9.4).
		Descriptive statistics of change from baseline	Extended Treatment Period Population	No comparison during Period 3	Other secondary efficacy analyses (Section 6.9.4).
Spinal Pain	Spinal Pain and Spinal Pain at night change and % improvement from baseline	MMRM	ITT Population	IXE80Q4W vs. placebo at Week 16 and all other postbaseline visits in Period 2	Other secondary efficacy analyses (Section 6.9.4).
		Descriptive statistics of change from baseline	Extended Treatment Period Population	No comparison during Period 3	Other secondary efficacy analyses (Section 6.9.4).

Measure	Variable	Analysis Method (Sections 6.1, 6.3)	Population (Section 6.1.5)	Comparison/Time Point	Analysis Type
CRP	CRP change from baseline	MMRM	ITT Population; ITT Population in bDMARD-naïve patients; Per Protocol Set; Per Protocol Set in bDMARD-naïve patients	IXE80Q4W vs. placebo at Week 16 and all other postbaseline visits in Period 2	Other secondary efficacy analyses (Section 6.9.4).
		Descriptive statistics of change from baseline	Extended Treatment Period Population	No comparison during Period 3	Other secondary efficacy analyses (Section 6.9.4).

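### Read as written, the SAP applies ASAS5/6 as a 5-of-5 rule instead of 5-of-6 at the 10 of 15 postbaseline visits where lateral spinal flexion is not scheduled

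*SAP*

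**What the plan says.** **The rule.** SAP Appendix 1 has three steps for ASAS5/6. Step 1 makes a patient a responder by the test "among the 6 domains (Patient Global, Spinal Pain, Function, Inflammation, CRP, Spinal mobility), if at least 5 of them are" at 20% improvement or better. Step 2 makes a patient a nonresponder if two or more non-missing domains fall short of 20%. Step 3 reads "for all other situations, assign ASAS5/6 response as missing". Percent improvement (V1) is itself missing when the observed value is missing.

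**The analysis visits.** In SAP Table RHCH.6.4 the row "ASAS5/6 and ASAS partial remission" is analysed by logistic regression and Fisher's exact test, both with NRI, for "IXE80Q4W vs. placebo at Week 16 and all other postbaseline visits in Period 2". For Period 3 the row gives descriptive response rates without a comparison. SAP Section 6.1.2 supplies the visits: categorical responses "will be summarized for all scheduled visits (NRI), including Week 52 (Visit 17) during Period 3". SAP Section 6.3.1 counts a missing response as nonresponse and adds "The NRI may be applied at any time point specified for analysis".

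**The data.** Protocol Section 9.1 names lateral spinal flexion as the spinal mobility domain, and Section 9.1.2.6 makes it a BASMI component: "The BASMI is a combined index comprising the following 5 clinical measurements of spinal mobility". The Schedule of Activities marks BASMI postbaseline at Weeks 8, 16, 24, 36 and 52 and at early termination. Patient Global, Spinal Pain, BASFI, BASDAI and CRP, which supply the other five domains, are marked at every postbaseline visit.

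**The concern.** The endpoint needs six domains, but at most of the visits named for its analysis only five are collected. The SAP has no rule for a domain that is absent by design. Its one provision on unscheduled variables, in Section 6.1.1, opens "For variables that are not collected at each postbaseline visit, data may exist at visits where the variable was not scheduled to be collected". That provision deals with stray early-discontinuation data in the repeated-measures model, not with composites.

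A missing component therefore passes through Step 3 and NRI as if it were a patient's missing visit. The definition of response would change from visit to visit, and the output would not show it, because Steps 1 and 2 still return responders and nonresponders from five domains. At stake are the Period 2 comparisons away from Weeks 8 and 16 and the shape of the Period 3 response curve.

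**Working it through.** The documents give no ASAS5/6 rate or power figure, so there is none to reproduce. The check has four steps.

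**1. Count the visits (Schedule of Activities).**
- Period 2 postbaseline: Weeks 1, 2, 4, 8, 12, 16 = 6 visits. Flexion at Weeks 8 and 16, so 6 − 2 = 4 without it (Weeks 1, 2, 4, 12).
- Period 3: Weeks 20 to 52 every 4 weeks = 9 visits. Flexion at Weeks 24, 36 and 52, so 9 − 3 = 6 without it (Weeks 20, 28, 32, 40, 44, 48).
- Total: 6 + 9 = 15 visits, of which 4 + 6 = 10 lack the sixth domain.

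**2. Run Appendix 1, then NRI, over every case.**

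| Collected domains met (of 5) | Flexion met | Flexion not met | Flexion not collected: Appendix 1 | Flexion not collected: after NRI |
|---|---|---|---|---|
| 5 | Responder | Responder | Responder | Responder |
| 4 | Responder | Nonresponder | Missing | Nonresponder |
| 3 or fewer | Nonresponder | Nonresponder | Nonresponder | Nonresponder |

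Of the 2^5 = 32 met/not-met patterns of the five collected domains, uncollected flexion gives the same result as flexion not met in all 32. It differs from flexion met in the 5 patterns with exactly four met. No pattern moves the other way. In each arm:

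shortfall in rate = P(exactly four of five met, and flexion would have been met)

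**3. A constructed patient.** Improvements are 45, 40, 30 and 25% in the four patient-reported domains and 10% in CRP. Flexion goes from 10 to 13 cm. With the BASMI linear score S = (21.1 − A)/2.1 from SAP Table RHCH.6.3:
- Baseline S = (21.1 − 10)/2.1 = 5.286. Observed S = (21.1 − 13)/2.1 = 3.857.
- V1 = 100 × (5.286 − 3.857)/5.286 = 27.0%, so flexion is met.
- At a visit with flexion (say Week 24), 5 of 6 domains are met: responder.
- At a visit without it (say Week 28) and with the other five values identical, 4 are met and 1 is below 20%. Step 1 and Step 2 both fail, Step 3 gives missing, and NRI gives nonresponder.

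This example needs the 0–10 score. V1 is baseline minus observed, over baseline, so raw centimetres would give 100 × (10 − 13)/10 = −30%, and a real improvement would count as worsening. Appendix 1 does not say which scale is used.

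**4. Can the shortfall be sized?** Not from the documents, which give no domain-level rates. On assumed inputs only (each of the five domains met by 30–70% of patients, flexion by 20–40%, latent correlation 0–0.6), the 5-of-5 rule loses about 6% to 82% of the patients who would respond under 5 of 6. At 50%, 40% and 0.3, the rate falls from 20.4% to 10.4%. The uncorrelated case can be checked by hand. With 50% and 40%, five of five is 0.5^5 = 0.031 and the lost group is 5 × 0.5^5 × 0.4 = 0.0625. The loss is then 0.0625/(0.031 + 0.0625), about 67%. A range this wide shows that the loss need not be trivial, but it is not an estimate.

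**The case against.** The strongest reply is that the visit phrase is stock wording. The same table uses it for BASMI, chest expansion, occiput-to-wall distance and MASES, which in Period 2 are collected postbaseline only at Weeks 8 and 16. The closest parallels are the binary rows for complete resolution of MASES and of heel enthesitis, which also use NRI. Taken literally, every patient in both arms would be a nonresponder there at Weeks 1, 2, 4 and 12, which cannot be meant. Likewise, the scheduled visits in Section 6.1.2 must depend on the measure, since WPAI-SpA and EQ-5D-5L have only Week 52 in Period 3. The phrase could apply to each variable in the shared row on its own schedule.

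This stands as evidence of intent, and it is why the point is conditional on reading the text as written. It does not settle the matter, for three reasons:
- The SAP narrows time points elsewhere: Week 16 for MRI, WPAI-SpA and EQ-5D-5L, and listed weeks for NSAID intake.
- The row is shared with partial remission, whose four domains are collected at every visit, so the wording is literally right for half the row.
- An enthesitis rate of zero would expose itself at once. An ASAS5/6 rate computed from five domains would look plausible.

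It is also fair that the same rule applies in both arms, and that six of the ten visits carry no test.

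**Conclusion.** The point holds as a conditional one. If the text is followed as written, ASAS5/6 is scored 5 of 5 at 10 of 15 postbaseline visits, and the rate there can only be understated. The affected output is four between-arm comparisons without multiplicity control (Weeks 1, 2, 4 and 12) and a descriptive Period 3 summary that would tend to rise at Weeks 24, 36 and 52 and fall between them for no clinical reason. The zigzag requires only that some patients have exactly four collected domains met plus flexion met.

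Three stronger readings are tempting, and the documents do not support them:
- **The SAP definitely intends all 15 visits.** The stock wording leaves the intent open.
- **The schedule would produce an apparent loss of response from Week 16 to Week 20, and so undermine the maintenance objective.** ASAS5/6 is not among the endpoints listed in Section 6.1.3 for combined Periods 2 and 3. The two periods use different populations, Period 3 is descriptive, and Week 52 itself has all six domains.
- **5 of 32 patterns is a share of patients.** It is a count of unweighted combinations.

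Week 16 and the primary and major secondary endpoints are untouched by this problem. It is worth correcting because the text as written gives a wrong rate and the correction is nearly free.

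**What to change.** Before the Week 16 unblinding:
- Give ASAS5/6 its own row in SAP Table RHCH.6.4, with time points Weeks 8 and 16 for Period 2 and Weeks 24, 36 and 52 for Period 3. Partial remission keeps the present wording.
- Add to Appendix 1: ASAS5/6 is derived only at visits where lateral spinal flexion is scheduled, and NRI applies only to missing data at those visits.
- As a separate clarification, state that flexion enters V1 as the 0–10 BASMI linear score. This matters at the five remaining visits too.

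The cost is one table row, a few lines in Appendix 1 and a visit filter in the program. No new data are needed, and the primary and major secondary analyses do not change.
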